### 16. SECONDARY ANALYSIS – IMMUNOGENICITY

The secondary objective of this study is to assess 2 methods of measuring *in vitro* neutralizing activity to metreleptin:

- 1. Cell-based assay
- 2. ECLIA receptor blocking assay

Document: Statistical Analysis Plan: AEGR-734-401: A 36-Month, Multicenter, Open Label Phase 4 Study to Evaluate the

Immunogenicity of Daily SC Metreleptin Treatment in Patients with Generalized Lipodystrophy

Author: [name], [name], [name], [name] Version Number: 2.1

*In vitro* neutralizing activity as measured by cell-based and ECLIA receptor blocking assays are fully described by the primary analysis (**Section 15.** Primary Analysis – Immunogenicity). There will be no formal comparison of the two assay methods. No further analyses are required to achieve the secondary objective. Additional data visualizations may be generated as needed.

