2.2 Rationale for Study Design, Doses and Control Groups

This study is being conducted to satisfy a postmarketing requirement to assess the immunogenicity associated with metreleptin treatment. Because immunogenicity can only be evaluated in the context of drug treatment, the study is open-label and will characterize antibody and *in vitro* neutralizing activity over time and will compare safety and tolerability in patients with different antibody statuses (e.g., binding antibody titer, *in vitro* neutralizing activity category, in vitro neutralizing activity percent inhibition). Immunogenicity will be evaluated in the context of the prescribing information for MYALEPT; thus, the patient population and dosing will be per the US prescribing information (MYALEPT Prescribing Information).

Anti-metreleptin and anti-HuL binding antibody titers over time will be evaluated in order to establish a time course of antibody development and to assess the development of antibodies that recognize the endogenous protein. Because samples from a few patients treated with metreleptin have demonstrated *in vitro* neutralizing activity in an *in vitro* cell-based assay, *in vitro* neutralizing activity will also be assessed in all antibody positive samples. To provide an orthogonal method to evaluate potential *in vitro* neutralizing activity, all antibody positive samples will also be assessed using a ligand-binding assay.

Safety and tolerability of metreleptin associated with the development of, or absence of, antibodies will be evaluated. All adverse events (AEs) will be collected throughout the course of this study. Serious adverse events (SAEs), adverse events of special interest

Confidential Page 17 of 60

(AESI) AEs leading to discontinuation, standard laboratory tests and vital signs will be collected over time and analyzed for any potential association with antibody status. See Section 8.2 for definitions of AEs and AESIs

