3.2 Secondary Objectives

Secondary Objective: Outcome Measure:

Assess 2 methods of measuring *in vitro* neutralizing activity to metreleptin.

Receptor-binding assay titer, cell-based assay category.

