6.4 Follow-up for Patients with *In Vitro* Neutralizing Activity

Patients identified with neutralizing activity during the 3-year study period will be encouraged to continue participation in the study and complete all protocol-specified assessments until the end of the study period (even if the decision is made to discontinue metreleptin). At the end of the 3-year study period, these patients should be enrolled in the separate MYALEPT Immunogenicity Follow-up program in order to continue immunogenicity assessments. Evidence of *in vitro* neutralizing activity will be considered either Category D or E results in the cell-based assay (refer to Section 7.3.3), or positive results based on percent inhibition (criteria to be determined) in the receptor-binding assay (refer to Section 7.3.2). Instructions for consent and enrollment into this separate Follow-up program will be provided by the Sponsor's safety physician.

Confidential Page 31 of 58

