10.2 Sample Size Estimate

Ten patients who have been prescribed metreleptin for generalized lipodystrophy will be included in this study; patients will be evaluated for a period of 3 years.

Pooled data from 2 previous studies of metreleptin for lipodystrophy (NIH 991265/20010769 and FHA101 [NCT00677313, FHA101]) indicated the proportion of patients who developed binding antibodies to metreleptin at titers ≥25 was 80% after treatment with metreleptin. If 10 patients are enrolled in this study, there is 87.9%

Confidential Page 45 of 58

certainty that a minimum of 6 out of the 10 patients will have a titer of binding antibody ≥25. The expected distribution of maximum titer for these 10 patients is presented in 5.

Table 5: Expected Number of Patients with Maximum Antibody Titer

MAXIMUM TITER	NUMBER OF PATIENTS
0	1
5	1
25	1
125	2
625	3
3125	2
15625	0

Studying 10 patients in this rare population is adequate to confirm previous immunogenicity results from both the obesity and lipodystrophy development programs. Following patients for 3 years should be adequate to assess time to peak titer since previous data suggest a range of 4 to 7 months. *In vitro* neutralizing activity will also be measured in all antibody positive samples, and may be detected by either the receptor cell-based assay or the ligand-binding assay (under development). However, if 0 out of 10 enrolled patients is observed with *in vitro* neutralizing activity, the point estimate (90% confidence interval) for the proportion of patients with neutralizing activity is 0.00 (0.00, 0.26) (computed in StatXact version 7.0). Because generalized lipodystrophy is a rare disease and events of *in vitro* neutralizing activity are infrequent, it is not feasible to gain a precise estimate of *in vitro* neutralizing activity; this study is not designed to determine this estimate

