10.5 Methods for Statistical Analyses

There will be no hypothesis testing. All data will be summarized by descriptive statistics and/or listings. In general, continuous variables will be summarized by n, mean, SD, median, min and max. Number of patients and percentage of patients in a category will be provided.

Descriptive statistics will be provided for immunogenicity variables (Section 10.4). The maximum antibody titer (anti-metreleptin or anti-HuL) during a visit will be summarized by visit. Categorization of *in vitro* neutralizing activity as assessed by cell-based assay will be summarized across visits; the rate of Category D and E *in vitro* neutralizing activity with 90% and 80% exact confidence intervals will be computed. The results are reported as percent inhibition and 80% inhibition is currently utilized as the neutralizing antibody threshold. activity Results for *in vitro* neutralizing activity will be summarized across visits; however, there will be no formal comparison of the 2 assay methods for the detection and relative potency of Category D or E *in vitro* neutralizing activity.

Maximum antibody titers, neutralizing activities detected by both methods, and metreleptin exposure for each patient will be plotted over time. Maximum antibody

Confidential Page 47 of 58

titers, neutralizing activities detected by both methods, and any associated clinical events (i.e., loss of efficacy or AE) will be summarized.

All AEs will be coded using the Medical Dictionary for Regulatory Activities (MedDRA). The number and percentage of patients who experienced at least 1 AE will be summarized by system organ class and preferred term. AEs will be summarized by relationship to the study medication and by severity. Deaths, SAEs, AESIs, and AEs leading to discontinuation will be tabulated and/or listed. SAEs, AESIs and AEs leading to discontinuation will be summarized respectively by peak antibody titers (antimetreleptin, anti-HuL) and by *in vitro* neutralizing activity categories or percent inhibition.

Clinical laboratory results (hematology, chemistry, and urinalysis), and vital signs results will be summarized using descriptive statistics for each visit.

Change from baseline in HbA1c and percent change from baseline in fasting triglycerides will be summarized for each visit by overall patient population, by peak antibody titers (anti-metreleptin, anti HuL), and by *in vitro* neutralizing activity categories or percent inhibition , respectively.

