### 4.3 Changes to Analysis from Protocol

There are no changes to the analysis from the protocol.

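### SAP Section 16 relies on separate assay summaries for the two-assay secondary objective and specifies no table pairing the two results on the same sample or patient

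*SAP*

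**What the plan says.** Protocol 3.2 makes the assessment of two neutralizing-activity assays the secondary objective and gives as outcome measures "Receptor-binding assay titer, cell-based assay category". Protocol 2.2 explains the second assay as an orthogonal method: beside the cell-based assay, "all antibody positive samples will also be assessed using a ligand-binding assay". Protocol 7.3.1 likewise applies both assays to every sample positive for binding antibodies.

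Protocol 10.5 rules out a formal comparison of the assays but plans two displays that bring them together. In the first, maximum titers, "neutralizing activities detected by both methods, and metreleptin exposure for each patient will be plotted over time". In the second, maximum titers, "neutralizing activities detected by both methods, and any associated clinical events (i.e., loss of efficacy or AE) will be summarized".

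SAP 15.2 summarizes the cell-based result (categories A to E, positive, high positive, ever, peak, time to) and the receptor-blocking (RB) result (positive, titer, percent inhibition, ever, peak, time to) in two separate lists. SAP 16 refers back to these, repeats that there is no formal comparison, and concludes: "No further analyses are required to achieve the secondary objective". Beyond that it allows only optional graphics. SAP 4.3 states: "There are no changes to the analysis from the protocol".

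**The concern.** The value of an orthogonal assay lies in whether it flags the same samples and patients as the first. Two lists of positivity rates show how often each assay is positive and nothing about overlap. The paired data exist by design, so the SAP leaves unused the information that bears most directly on its own secondary objective.

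The protocol's both-method displays would have shown part of this, and the SAP text does not name them. An analyst working from the SAP text alone could meet every stated requirement without producing any output that puts the two assays together.

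The overlap also matters for counting cases. Protocol 10.2 says neutralizing activity "may be detected by either the receptor cell-based assay or the ligand-binding assay". For follow-up enrolment, Protocol 6.4 says evidence of activity "will be considered either Category D or E results in the cell-based assay", or a positive receptor-binding result. A count of patients positive on either assay depends on the overlap, not only on the two separate rates.

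**Working it through.** **1. Are the data paired?** Yes. Protocol 2.2 and 7.3.1 run both assays on each antibody-positive sample. Protocol Table 1 schedules ten post-dose antibody samples per patient (Visits 3 to 12). The ceiling is therefore 10 × 10 = 100 samples for the protocol's ten patients, or 10 × 11 = 110 for the SAP's eleven, before restriction to antibody-positive samples.

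**2. Protocol displays against the SAP text.**
- Per-patient plot over time of titers, both assays and exposure: not named in SAP 15 or 16, which mention only graphics as needed.
- Summary of titers, both assays and clinical events: partly covered. SAP 17.1 breaks adverse events down by each assay separately, without pairing. The loss-of-efficacy part has no counterpart by neutralizing activity, because SAP 18.2 presents effectiveness by visit only.
- Same-sample cross-table: in neither document.

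**3. The plan's own figure.** The plan gives no figure for agreement. Its one figure for neutralizing activity is the 90% exact interval for 0/10 in Protocol 10.2. The upper limit is 1 − 0.05^(1/10) = 0.259, which reproduces the stated 0.26.

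**4. What separate rates leave open.** Let n paired results have a positive on the cell-based assay, b positive on RB, and j positive on both. Then:
- agreement = (n − a − b + 2j)/n
- positive on either = a + b − j

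The values of a and b below are assumed, since the documents give none.

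| a = b, n = 10 | j | Agreement | Positive on either |
|---|---|---|---|
| 1 | 0 | (10 − 2 + 0)/10 = 80% | 2 |
| 1 | 1 | (10 − 2 + 2)/10 = 100% | 1 |
| 3 | 0 | (10 − 6 + 0)/10 = 40% | 6 |
| 3 | 1 | (10 − 6 + 2)/10 = 60% | 5 |
| 3 | 2 | (10 − 6 + 4)/10 = 80% | 4 |
| 3 | 3 | (10 − 6 + 6)/10 = 100% | 3 |

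In all four rows with 3/10, the SAP 15.2 tables would print the same line for both assays: 30%, with a 90% exact interval of 8.7% to 60.7%.

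The base may be smaller than 10, because antibody-negative patients are not tested on either assay. Protocol Table 5 expects one patient in ten at titer 0. With n = 9, the range is (9 − 2)/9 = 78% or 100% for one positive on each assay, and (9 − 6)/9 = 33% to 100% for three.

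**5. Cut-offs.** SAP 15.2 calls RB positive when activity is detected at the 1:6 minimum dilution. Protocol 7.3.3 and 10.5 use 80% inhibition as the neutralizing threshold. The documents do not say whether the two criteria coincide, and any paired table depends on the answer.

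**The case against.** The strongest reply is that the SAP does what the protocol asks. The outcome measures are the two readouts, both are summarized in full, and both documents exclude a formal comparison. Neither promises a same-sample table. That stands, and it is why this is a weakness rather than a breach. It does not rule out a descriptive count table, which involves no formal comparison.

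A reader might infer that the Protocol 10.5 displays have been dropped. The documents do not support that. SAP 4.3 declares no changes, and SAP 2 gives the SAP precedence only where methods differ, so silence can be read as leaving the displays in force. SAP 9 leaves the format and content of outputs to a shell document, which was not available for this review; nor were parts of the change record. What can be said is that the SAP text does not name them.

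A reader might also infer that the number of patients positive on either assay could not be recovered. That goes too far. The first adverse event of special interest in SAP 17.1 covers Category D or E activity or the corresponding ligand-binding result, and SAP 8.1 provides for listings, which with 10 or 11 patients could show both results. The route is only partial: it relies on event reporting, leaves out Category C, and does not define the corresponding ligand-binding result. Protocol 6.4 is also a rule for entering the follow-up program, not an analysis endpoint.

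Finally, the illustrative rates are hypothetical. Protocol 10.2 calls neutralizing activity infrequent, so 3/10 on each assay may be high. At 1/10 on each, the uncertainty is whether the positives are one patient or two.

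**Conclusion.** The point holds as an inexpensive improvement. SAP 16 declares separate summaries sufficient for an objective about two assays run on the same samples, specifies no paired table, and does not name the protocol's both-method displays. With 10 paired results, the unresolved range of agreement is 20 percentage points (80% or 100%) at one positive per assay and 60 points (40% to 100%) at three. These sizes rest on assumed rates; the underlying fact, that two separate rates do not fix their overlap, does not. The conclusion is confined to the SAP text and does not extend to what the shells or final outputs contain.

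**What to change.** In SAP 16, replace the sentence that closes off further analysis with two descriptive tables:

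- **By sample:** cell-based category (A to E) against RB result on the same samples, as counts by visit. Match on the sample itself. SAP Appendix 2 keeps one assessment of each type per window, so matching after that selection could pair different draws.
- **By patient:** the same cross-tabulation for ever-positive and peak results, with raw agreement and the number positive on either assay.

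Use no test, and give no confidence interval for sample-level agreement, because repeat samples from one patient are not independent. Name the Protocol 10.5 per-patient plots and both-method summary as planned outputs. State the RB cut-off used and whether detection at 1:6 is the same as 80% inhibition; if not, show the tables under both.

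The cost is two small tables and a few sentences, from data already collected. The tables will be sparse with 10 or 11 patients. The change record shows that the database is already locked, so they must be labelled post-lock descriptive additions.

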#### 17. SAFETY OUTCOMES

All outputs for safety outcomes will be based on the SAF.

#### 17.1 Adverse Events

Adverse Events (AEs) will be coded using the latest version of MedDRA, and summarized by SOC, preferred name, and intensity. Intensity is captured in the CRF. See **Section 8.1** Statistical Tests and Confidence Intervals for a description of summaries to be reported.

Adverse Events of Special Interest (AESIs) are defined as:

- The presence of Category D or E *in vitro* cell-based NAb activity (or the relevant corresponding test result from the ligand-binding method) to metreleptin
- Necrotizing pancreatitis
- Hepatic adverse events including potential drug induced liver injury (DILI)
- Severe hypoglycemia
- Severe hypersensitivity reactions
- New diagnoses of autoimmune disorders (for instance, autoimmune hepatitis, glomerulonephritis, lupus erythematosus, antiphospholipid antibody syndrome, rheumatoid arthritis)
- Autoimmune disease exacerbation
- Serious infection resulting in hospitalization
- All cancers (excluding non-melanoma skin cancer) by cancer type
- Exposed pregnancies and pregnancy outcomes.

TEAEs are defined as AEs that started or worsened in severity on or after the first dose of study medication. If it is unclear whether or not an AE is a TEAE due to partial dates, the worst case will be assumed (i.e., TEAE). See **Appendix 1** for handling of partial dates.

AEs, serious AEs (SAEs), AEs of special interest (AESIs), TEAEs, AEs possibly caused by metreleptin, and AEs leading to metreleptin discontinuation will be summarized by ADA positivity and titer, cell-based NAb positivity and titer, and RB positivity, titer, and quintile of percent

Document: Statistical Analysis Plan: AEGR-734-401: A 36-Month, Multicenter, Open Label Phase 4 Study to Evaluate the

Immunogenicity of Daily SC Metreleptin Treatment in Patients with Generalized Lipodystrophy

Author: [name], [name], [name], [name] Version Number: 2.1

inhibition. For each patient, only one event of each type will be selected to include in summary outputs. If a patient has multiple events the same type, the event with the highest severity level is selected. For patients with multiple events of the same type and severity, the event corresponding to the highest titer or percent inhibition level is selected. The corresponding titer and percent inhibition level are defined by the most recent measurement occurring prior to the event start date.

See **Section 8.1** Statistical Summaries, Tests and Confidence Intervals for a description of statistics to be reported. Additional data visualizations may be generated as needed.

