8.2 Definitions of Serious Adverse Events

An SAE is an AE occurring during any study phase (i.e., run-in, treatment, wash-out, follow-up), that fulfills one or more of the following criteria:

- Results in death
- Is immediately life-threatening
- Requires in-patient hospitalization or prolongation of existing hospitalization
- Results in persistent or significant disability/incapacity or substantial disruption of the ability to conduct normal life functions
- Is a congenital abnormality or birth defect
- Is an important medical event that may jeopardize the patient or may require medical intervention to prevent one of the outcomes listed above

For further guidance on the definition of an SAE, refer to Appendix A.

In addition, for the purposes of this protocol, the following adverse events of special interest (AESI) must be handled as SAEs and are reportable to Aegerion or designee (see Section 8.6) within the SAE timeframe regardless whether the adverse events did not meet the serious criteria described above in this section:

- The presence of Category D or E *in vitro* neutralizing activity (or the relevant corresponding test result from the ligand-binding method) to metreleptin
- Necrotizing pancreatitis
- Hepatic adverse events including potential DILI

Confidential Page 37 of 58

- Severe hypoglycaemia
- Severe hypersensitivity reactions
- New diagnoses of autoimmune disorders (for instance, autoimmune hepatitis, glomerulonephritis, lupus erythematosus, antiphospholipid antibody syndrome, rheumatoid arthritis)
- Autoimmune disease exacerbation
- Serious infection resulting in hospitalization
- All cancers (excluding non-melanoma skin cancer) by cancer type
- Exposed pregnancies and pregnancy outcomes

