Positive NAb activity will be defined as a titer category C, D, or E result. High positive NAb activity will be defined as a a titer category D or E result. Category D and E results are considered to represent

Document: Statistical Analysis Plan: AEGR-734-401: A 36-Month, Multicenter, Open Label Phase 4 Study to Evaluate the

Immunogenicity of Daily SC Metreleptin Treatment in Patients with Generalized Lipodystrophy

Author: [name], [name], [name], [name] Version Number: 2.1

high potency NAb activity. The clinical relevance of NAb activity results in any category has not been determined, and is a topic of current investigation. The following information will be summarized:

- Ever NAb positive and time to NAb positivity. Time to NAb positivity (months) = [((date of first NAb positive result date of baseline visit) + 1)/30.4].
- Ever high NAb positive and time to high NAb positivity. Time to high NAb positivity (months) = [((date of first hight NAb positive result date of baseline visit) + 1)/30.4].
- Peak NAb (defined as the measurement which detects NAb activity at the largest dilution factor) and time to peak NAb. Time to peak NAb activity (months) = [((date of peak NAb date of baseline visit) + 1)/30.4].

RB activity of anti-metreleptin/anti-HuL will be assessed by ECLIA receptor blocking assay and reported as follows:

- Positive/negative for RB activity by study visit. Positive RB activity is defined as RB activity detected at MRD (1:6 dilution factor). Both 90% and 80% two-sided Exact CIs will be presented.
- RB activity by study visit and titer (negative [no RB activity detected at MRD], 1:6, 1:30, 1:300, 1:3000). Dilution factors greater than 1:3000 will not be examined.
- Percent inhibition at MRD by study visit
- Ever RB positive and time to RB positivity. Time to RB positivity (months) =  $[((date \ of \ first \ RB \ positive \ result date \ of \ baseline \ visit) + 1)/30.4].$
- Peak RB (defined as the measurement which detects RB activity at the largest dilution factor) and time to peak RB. Time to peak RB result (months) = [((date of peak RB date of baseline visit) + 1)/30.4].

See **Section 8.1** Statistical Summaries, Tests and Confidence Intervals for a description of statistics to be reported.

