### Changes documented in 16Dec2024 version (prior to DBL)

1. Update definition of EAS from:

[E]nrolled subjects who received at least one documented dose of metreleptin and who have baseline and post-dose laboratory results on the measure of interest at the time point of interest.

To:

Enrolled subjects who received at least one documented dose of metreleptin and who have at least one anti-metreleptin/anti-HuL binding antibody (Antidrug Antibody (ADA) binding) result.

2. Update the following analysis from:

AEs, serious AEs (SAEs), AEs of special interest (AESIs), TEAEs, AEs possibly caused by metreleptin, and AEs leading to metreleptin discontinuation will be summarized by ADA positivity and titer, cell-based NAb positivity and titer, and RB positivity, titer, and quintile of percent inhibition.

To:

TEAEs, serious TEAEs, TEAEs that are AEs of special interest (AESIs), TEAEs possibly caused by metreleptin, and TEAEs leading to metreleptin discontinuation will be summarized by ADA positivity and titer, cell-based NAb positivity and titer, and RB positivity, titer, and quintile of percent inhibition.

3. Update analysis windows such that data collected for a CRF-defined visit are windowed according to the CRF-defined visit. Previously analysis windows ended on the same day as CRF-defined visit windows and extended CRF-defined windows to cover the calendar space since the last CRF-defined visit. Analysis windows are updated to extend CRF-defined visit windows to cover calendar space on either side of the CRF-defined visit window. See updated windows in Table 1 below.

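### Category D/E neutralizing activity is counted as an AESI and also defines strata of the AESI and TEAE tables, so those tables mix an assay result into the clinical event counts

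*SAP*

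**What the plan says.** **The event.** Protocol 8.2 and SAP 17.1 each list ten AESIs. Nine are clinical conditions or outcomes. The first is a laboratory finding: "The presence of Category D or E *in vitro* cell-based NAb activity (or the relevant corresponding test result from the ligand-binding method) to metreleptin". Protocol 8.2 adds that AESIs "are reportable to Aegerion or designee (see Section 8.6) within the SAE timeframe regardless whether the adverse events did not meet the serious criteria", so the result is reported on the SAE clock even when it meets no seriousness criterion.

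**The strata.** SAP 17.1 states that AEs, SAEs, AESIs and TEAEs "will be summarized by ADA positivity and titer, cell-based NAb positivity and titer, and RB positivity, titer, and quintile of percent" inhibition. Item 2 of the change form (16 December 2024, before database lock) narrows the tables to treatment-emergent events but keeps the AESIs: "TEAEs that are AEs of special interest (AESIs), TEAEs possibly caused by metreleptin, and TEAEs leading to metreleptin discontinuation will be summarized by ADA positivity", with the NAb and RB strata as before. SAP 15.2 uses the AESI criterion for one of its classes: "High positive NAb activity will be defined as a a titer category D or E result".

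**Linking event to stratum.** SAP 17.1: "The corresponding titer and percent inhibition level are defined by the most recent measurement occurring prior to the event start date". Each patient contributes one event per type. The most severe is kept, and among equals "the event corresponding to the highest titer or percent inhibition level is selected".

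**The protocol.** Section 10.5 groups differently: "SAEs, AESIs and AEs leading to discontinuation will be summarized respectively by peak antibody titers", and by neutralizing category or percent inhibition, with no time lag. SAP section 2 gives the SAP precedence where methods differ, yet SAP 4.3 declares no change from the protocol.

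**The concern.** The first safety objective is to relate safety and tolerability to the presence or absence of antibodies and neutralizing activity. Both documents say that the clinical relevance of neutralizing activity is not yet known, and the stratified tables are part of the planned evidence on it. If the assay result is itself one of the events, an any-AESI or any-TEAE count can differ between strata when no patient has had a clinical event. With about 11 patients, one such entry can change what a row appears to say.

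No text available to us removes the laboratory item from these tables or asks for a version restricted to clinical AESIs. A D/E result first found after dosing in a previously untreated patient also meets the SAP's TEAE definition if it is recorded as an adverse event, so the TEAE counts are affected too.

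**Working it through.** **Inputs.** AESI list: Protocol 8.2, SAP 17.1. Strata: SAP 17.1, change item 2, Protocol 10.5. D/E as high positive: SAP 15.2. Planned number: 11 (SAP 4.1; the protocol says 10). The documents give no expected number of D/E patients, so k = 1 to 3 is assumed.

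**Interval check.** The only stated figure on the frequency of neutralizing activity is the two-sided 90% exact interval for 0 of 10 in Protocol 10.2, 0.00 to 0.26. The upper limit is 1 − 0.05^(1/10) = 0.259, which reproduces it. The limits below use the same method: for 0/n the upper limit is 1 − 0.05^(1/n), and for k/k the lower limit is 0.05^(1/k).

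**Step 1. Following one patient.** Take successive samples with categories A, C, D, D and no clinical event. A measurement is dated by its sample.

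| Rule | Event kept | Last earlier result | Stratum |
|---|---|---|---|
| SAP 17.1, onset = sample date, first D/E result only reported | third sample | C | C, below D/E |
| SAP 17.1, onset = report date | third sample, reported later | D (third sample itself) | D/E |
| SAP 17.1, onset = sample date, both D results reported at equal severity | fourth sample, by the highest-titer rule | D | D/E |
| Protocol 10.5, grouped by highest category | any | not used | D/E |

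In the first row the earlier result cannot be D/E, because the event is the first D/E result. It may be A, B or C, or absent if the earlier sample had no neutralizing test. In every row the patient counts as having an AESI without any clinical event.

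Protocol 8.3.3 collects a start date and time for each AESI, but neither document says what the start date is when the AESI is only a laboratory result. The choice among the first three rows is therefore open.

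**Step 2. Size under Protocol 10.5, grouping by highest category, no clinical AESI in anyone.**

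| k (assumed) | D/E group (90% CI) | Others (90% CI) |
|---|---|---|
| 1 | 1/1 (0.05–1.00) | 0/10 (0.00–0.26) |
| 2 | 2/2 (0.22–1.00) | 0/9 (0.00–0.28) |
| 3 | 3/3 (0.37–1.00) | 0/8 (0.00–0.31) |

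With the laboratory item removed, the D/E row becomes 0/k.

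**Step 3. Size under SAP 17.1.** With sample-date onset and first events only, 0 of the k laboratory events fall in D/E and all k fall in lower or untested strata. With report-date onset, all k fall in D/E. With repeat events the result lies between these and depends on how many patients have consecutive D/E samples. The SAP does not say which denominator belongs to a stratum assigned by event, so only counts are given.

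**Step 4. The ADA tables.** Protocol 7.3.1 and SAP 15.1 confine routine neutralizing tests to ADA-positive samples. If patients are grouped by whether they were ever ADA-positive, routine testing cannot produce this AESI in the ADA-negative group. The item is thus tied to ADA status as well, though less directly than to NAb.

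**Step 5. The ligand-binding counterpart.** Protocol 7.3.3 uses 80% inhibition as the threshold, while SAP 15.2 calls RB positive when activity is detected at the minimum required dilution. SAP 17.1 does not say which of these corresponds to D/E. A sample detected at that dilution with less than 80% inhibition would be an AESI under one reading and not under the other.

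**The case against.** The strongest reply is that the SAP governs, and its lagged assignment was presumably meant to stop an event from being explained by a later antibody result. A reader might infer that every D/E patient has an AESI by construction and that the tables are simply circular. The documents do not support that as a general statement. It follows from Protocol 10.5, which the SAP replaces, and even there the word for peak is attached to antibody titers, so grouping by highest neutralizing category is an assumption. The opposite inference, that no first D/E event can appear in the D/E stratum, fails too: it needs sample-date onset and sets aside the highest-titer rule.

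Other parts of the reply also stand:

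- SAP 17.1 summarizes by system organ class and preferred name, so the laboratory item may have its own row and leave the clinical rows readable. The table shells and parts of the change form are not available, so this cannot be checked.
- It would be too strong to say that nothing in the plan can relate neutralizing activity to clinical course. Protocol 10.5 also plans patient plots over time, a summary with associated clinical events, and HbA1c and triglyceride changes by neutralizing category.
- Handling AESIs as SAEs is a reporting rule. Seriousness is a separate field, so serious-TEAE counts change only if the item is flagged serious.

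It can also be said that binding titer does not define the D/E item, so the ADA tables should keep it. That is weaker, given Step 4. The relation between titer and neutralizing activity is of interest, but it is better shown directly than through an adverse event count.

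**Conclusion.** The concern holds in this form: the same laboratory result is a counted event and a stratum criterion, and no visible text separates the two roles. Under the governing SAP rule the outcome is either misfiling into a lower or untested stratum or placement in D/E by construction, depending on an undefined onset date and on whether repeat results are reported. Any-AESI and any-TEAE counts by antibody status therefore do not cleanly show whether neutralizing activity goes with clinical events.

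The effect is one patient in a stratum count for each D/E patient. It rests on these assumptions: at least one D/E result occurs, it is recorded as an AESI as the protocol requires, and the unseen shells do not already remove it. One of ten AESI items is affected, there is no hypothesis testing, and the primary immunogenicity analysis is untouched. Severity: should-fix.

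**What to change.** In SAP 17.1 and change item 2:

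1. Exclude the laboratory-defined AESI from the AESI and TEAE tables stratified by NAb, RB or ADA, and from the serious-TEAE tables if it has been flagged serious.
2. Report it separately in an unstratified line and a listing, with its relation to ADA titer shown descriptively.
3. State its onset date (sample or report) and which ligand-binding result corresponds to D/E, reconciling Protocol 7.3.3 with SAP 15.2.
4. Record in SAP 4.3 both this change and the move from the Protocol 10.5 grouping to assignment by the last earlier result.

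Leave expedited reporting unchanged. The change form already carries entries made after database lock, so the same route can be used, with the timing stated.

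Cost: a few sentences and a program filter, with no new data. The stratified AESI counts become slightly smaller.
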